6.1.2. Handling of Missing Data

In general, the observed case (OC) data for a visit will consist of the actual observations recorded for the visit. If missing, the OC data will remain missing — no missing imputation will be performed. Safety analyses will be conducted on the OC data only. However, imputation of missing AE and concomitant medication onset and stop dates will be used to determine the status of each AE and the prior/concomitant status of each medication. Please refer to [Section 5.2.1](#) for the method of imputation of missing AE onset and stop date and [Section 6.2.5](#) for the method of imputation of missing concomitant onset and stop dates.

For demographic and baseline characteristics, each variable will be analyzed and/or summarized using the available data. Patients with missing data will be excluded only from analyses for which data are not available.

6.1.3. Visit Windowing

It is expected that there will be a variation between patients in the actual number of study days from the start of administration of study drug within each cycle – defined as Day 1 – to the dates that the scheduled visits occurs. To handle this, for tables and figures where data are grouped by visit, assessments will be categorized using visit windows based on study days (relative to the Day 1 of each cycle). The visit-window mapping is described in [Table 20](#). Visit-based summaries will be based on the windowed visits. All data, whether or not within the visit windows, will be presented in patients listings.

For windowed visits during the treatment cycles, if more than 1 visit occurs during a visit window, the visit closest to the scheduled day will be assigned to the windowed visit. If two visits are equidistant from the scheduled day, the later visit will be assigned to the windowed visit. If there are multiple assessments on the same day, the worst case will be used. For the assigned follow-up visit, the last assessment in the window will be included in the summary.

For a patient who prematurely discontinues the study, the visit will be slotted accordingly. The window for post-treatment visit will be "the first dose date of the last cycle + 36 to last assessment date prior to the start of survival follow-up". For the survival follow-up visit, it will only be applicable for the hematologic parameters.

Table 20 Visit Windowing

Visit	Cycle 1/ Odd cycle (2X-1)						Cycle 2/ Even cycle (2X)						Post-treatment	Survival follow-up [e]
	C1D1	C1D3	C1D8	C1D10	C1D15	EOC1	C2D1	C2D3	C2D8	C2D10	C2D15	EOC2		
Scheduled Day [a]	1	3[f]	8[f]	10[f]	15	22	1	3[f]	8[f]	10[f]	15	22		
ECOG	Day 1						Day 1							
Clinical Chemistry [b]	Day -3 - 1		1-11		12- EOC		Day -3 - 1		1-11		12- EOC		First dose date of last cycle + 36 to last assessment date prior to the start of survival follow-up	Relative to the date of post-treatment, the last assessment falling in the window between 1 and 67.
Hematology [c]	Day -3 - 1	1 to 5	6 to 9	10 to 12	13 to 18	19 to EOC	Day -1 - 1	1 to 5	6 to 9	10 to 12	13 to 18	19 to EOC		
Urinalysis [b]	Day -3 - 1						Day -3 - 1							
FACT-L and FACT-An [d]	Day -1 - 1			1 to EOC			Day -1 - 1			1 to EOC				

[a] The scheduled day is relative to the Day 1 of each cycle.

[b] Hematology, clinical chemistry and urine analysis may be obtained up to 72 hours prior to the first dose of each cycle of G1T28 or placebo + E/P therapy.

[c] Hematology may be obtained up to 3 days prior to first dose of G1T28/placebo + EP therapy in Cycle 1, and 1 day prior to first dose for subsequent cycles.

[d] Patient-reported outcomes should be completed at Days 1 and 10 of each cycle and at the Post-Treatment Visit. If a cycle is delayed, the patient should still complete the PRO on the scheduled Day 1 of the next cycle, as well as the actual first dosing day of the next cycle of G1T28 or placebo + E/P therapy. Patient-reported outcomes may be obtained up to 24 hours prior to the first dose of each cycle of G1T28 or placebo + E/P therapy.

[e] 60 ± 7 days after the post-treatment visit only for hematologic parameters and immunologic biomarker. The data is collected only for patients in Part 2.

[f] If Day 1 is included in the windowing, the associated assessment must be post G1T28 infusion.

Note: The end date of a cycle (EOC) is defined as the date of Day 1 study drug administration of its next cycle. For the last cycle (where no subsequent cycle is given), the end of cycle will be defined as Day 36 relative to the first dose of the cycle. Hence, for the last cycle, the window for EOC is 19-36.

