#### 13.4.2.5. Analysis of Exploratory Efficacy Endpoints

Grade 2 or higher nephrotoxicity, alopecia, and mucositis will be summarized with the number and percentage of patients experiencing the event any time during the Treatment Phase. For tabulations performed based on data collected in Part 2, the difference between treatment groups will be calculated and reported as described for the incidence of hematologic toxicity.

The FACT scores will be calculated per the FACIT version 4 scoring instructions and summarized by visit. The change from baseline in each score will be calculated and presented at each postbaseline visit. Additionally the change from predose to Day 10 and change from predose to end of cycle values will be calculated and presented at each cycle. Analysis of covariance models may be performed for summaries on Part 2, similarly to those described in Section 13.4.2.1. The extreme (best and worst) onstudy values and minimum and maximum change will also be analyzed. The number and percent of patients that have clinically relevant improvements or deteriorations will be summarized.

A single composite endpoint taking into account multiple types of hematologic parameters and other clinically relevant measures is of interest to capture the efficacy of G1T28 + E/P therapy. A composite endpoint will be defined *a priori* in a SAP. Factors such as infection rate, toxicity rates, chemotherapy dose reductions and/or interruptions, incidence of transfusions, incidence of growth factor use, AUC, etc. may be included. The association between composite endpoints and best overall response, overall survival, and PFS may be explored.

Similarly, identifying a composite hematologic score that represents ANC, lymphocytes, platelets, and hemoglobin in a meaningful way will be defined *a priori* in the SAP.

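### The FACT Day 10 window in SAP Table 20 runs to the end of the cycle, so a much later form can be summarised as Day 10, and an on-time Post-Treatment form misses its own window

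*SAP*

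**What the plan says.** FACT-L and FACT-An have three kinds of scheduled form: "Patient-reported outcomes should be completed at Days 1 and 10 of each cycle and at the Post-Treatment Visit" (SAP Section 6.1.3, Table 20, note d). If a cycle is delayed, the patient completes a form on the scheduled Day 1 and another on the actual dosing day.

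For FACT, Table 20 has two windows per cycle: Day -1 to 1 under Day 1, and 1 to EOC under Day 10. There is no FACT window for the end of the cycle. On EOC the table note says "The end date of a cycle (EOC) is defined as the date of Day 1 study drug administration of its next cycle". A different rule covers a patient's final cycle: "the end of cycle will be defined as Day 36 relative to the first dose of the cycle". Note f adds "If Day 1 is included in the windowing, the associated assessment must be post G1T28 infusion", so the same cycle's predose form cannot fill Day 10.

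Within a window, "if more than 1 visit occurs during a visit window, the visit closest to the scheduled day will be assigned to the windowed visit"; ties go to the later visit. No maximum distance is given. "Visit-based summaries will be based on the windowed visits". The post-treatment window opens at the first dose date of the last cycle plus 36.

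Protocol Section 13.4.2.5 asks for the "change from predose to Day 10" and, as a separate quantity, the change from predose to end of cycle.

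**The concern.** Day 10 is the only scheduled mid-cycle FACT form. A window that stays open until the next cycle starts lets a form from the end of the cycle, or from the Post-Treatment Visit, be reported as mid-cycle. The two changes that the protocol keeps apart would then be partly built from the same kind of form. If patients who miss Day 10 differ from those who complete it, the Day 10 summary would mix two time points in a way that the reader of a table could not see.

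The last cycle adds a second problem. FACT has no end-of-cycle window to catch a form completed by Day 36, so a Post-Treatment form in that range is mapped to Day 10.

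**Working it through.** **Reproducing the plan's Day 36.** The Post-Treatment Visit is 30 days (+3) after the last dose (Protocol Table 9-1, note b). With the last dose on Day 3, the latest day is 3 + 30 + 3 = Day 36, which agrees with the SAP's end of the last cycle.

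**Inputs.** Scheduled day 10; window Day 1 to EOC; EOC at Day 22 for an on-time cycle, up to 22 + 14 = Day 36 for the longest permitted delay of 2 weeks, and Day 36 in the last cycle.

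**Which form takes the Day 10 label if the Day 10 form is missing.** Distance = form day − 10; the smallest distance wins.

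| Situation | Other forms | Form labelled Day 10 | Days late |
|---|---|---|---|
| Delayed 7 days | Days 22 and 29 | Day 22 (distance 12, against 19) | 12 |
| Delayed 14 days | Days 22 and 36 | Day 22 (distance 12, against 26) | 12 |
| Last cycle, last dose Day 3 | Post-Treatment, Days 33 to 36 | Post-Treatment | 23 to 26 |
| On time, next form on dosing day | Day 22 | Day 22 if EOC is inclusive; none if exclusive | 12 |
| On time, next form the day before | Day 21 | Day 21 on either reading of EOC | 11 |

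In both delayed rows the Day 22 form lies well outside the next cycle's Day -1 to 1 window, so Day 10 is the only window it fits. In the on-time rows the form also sits in the next cycle's Day 1 window. Substitution there needs a form to be allowed to serve two windows, which the SAP does not address.

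If the last dose is on Day 1 instead, the Post-Treatment Visit falls on Days 31 to 34, still inside the last-cycle window.

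**If the Day 10 form is present**, it has distance 0 and is chosen in every row. The closest-visit rule works as intended there.

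**Post-Treatment form and its own window.** First dose date + 36 is Day 1 + 36 = Day 37. An on-time visit after a Day 3 last dose is on Days 33, 34, 35 or 36, all before Day 37. With Day 10 present, the Post-Treatment form loses to it and appears in no visit summary. With Day 10 missing, it is reported as Day 10. Either way the Post-Treatment FACT summary loses it. This reads the post-treatment window as applying to FACT, because the text of Section 6.1.3 states it for the visit and not for particular parameters.

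**Width.** Days 1 to 22 is 22 days, and Days 1 to 36 is 36 days. The Day 10 hematology window in the same table is Days 10 to 12, or 3 days.

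**Check of a bounded window.** With Days 10 to 12 or Days 6 to 15, none of the late forms above (Days 21, 22, 29, 33 to 36) is eligible, and a form on Day 10 is still selected.

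**The case against.** The strongest case against runs as follows. The closest-visit sentence applies when a window holds more than one visit, and it then picks the Day 10 form correctly. A single contiguous window is also a convention within the same table: clinical chemistry, with two assessments after Day 1, uses 1-11 and 12-EOC, while hematology has narrow windows because it has several draws. Protocol Section 11.6 allows the Day 10 form to be given by phone, which should reduce missing forms among patients too unwell to attend. FACT is exploratory and summarised descriptively only (SAP Section 6.2.7.2), and SAP Section 7 drops the ANOVA on FACT scores. All data, inside or outside windows, are listed.

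Most of this stands, and it limits the importance of the point. It does not remove the fault. The substitution comes from the width of the cell with no distance limit, not from the closest-visit sentence alone. Chemistry splits its range at Day 11/12, so a Day 22 sample does not compete for the Day 8 slot; FACT has no second window to take the late form. Reading EOC as exclusive cures only the on-time form completed on the dosing day and a Post-Treatment form on Day 36. It leaves the delayed-cycle Day 22 form and the Post-Treatment form on Days 33 to 35. The SAP's own last-cycle window of 19-36 also points to an inclusive reading.

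A reader might infer that the SAP contradicts Section 6.1.2, under which "the OC data will remain missing". It does not, strictly: assigning an observed form to a declared window is not imputation, although it does defeat the evident purpose of that rule.

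**Conclusion.** The window is wrong as written, with minor impact. When the Day 10 form is missing and another form exists, a form 12 days late (delayed cycle) or 23 to 26 days late (last cycle, Day 3 last dose) can be summarised as Day 10. An on-time Post-Treatment FACT form does not reach the Post-Treatment summary. No test, sample size or prospectively defined endpoint is affected.

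Three stronger readings are not supported:

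- **That the substitute always reflects recovered counts.** This fits a form from the next dosing day, when the ANC and platelet criteria must be met. In a cycle delayed for hematologic toxicity the selected Day 22 form predates recovery, and no count criterion applies at the Post-Treatment Visit.
- **That every missing Day 10 form is replaced, with the next predose form used twice.** Another form must exist, and the SAP does not say whether one form may fill two windows.
- **That the dilution can be sized.** Assuming 10 to 30% missing Day 10 forms, a substitute for each and full recovery from a mid-cycle drop d gives an understatement of 0.1d to 0.3d, but this only returns the assumptions. The documents give no missing rate, no drop and no difference between arms.

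The "change from predose to Day 10" is named in the protocol and is not among the analyses that SAP Section 7 removes, though SAP Section 5.1.2.3 does not name it. If it is not produced, the fault still affects the by-visit FACT tables.

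**What to change.** In SAP Table 20:

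1. Replace 1 to EOC for FACT with a bounded window around Day 10. Days 6 to 15 is an illustration; the documents do not fix the limits.
2. State that a form belonging to the next cycle's Day 1, scheduled or actual, or to the Post-Treatment Visit cannot fill Day 10.
3. Assign Post-Treatment FACT forms to the Post-Treatment Visit even when they fall on or before Day 36.

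The cost is a change to the window text and its programming. Some Day 10 values will become missing, which shows the reader how many mid-cycle forms were actually collected.

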**Table 9-1 Schedule of Assessments**

Cycle Day	Screening	Enroll	Cycle 1 and Every Odd Cycle a (21 days)					Cycle 2 and Every Even Cycle a (21 days)					Last Cycle	Post-Treatment Visit b	Survival Follow-up c		
	-14	-3 to 1	1	2	3	8	10	15	1	2	3	8	10	15	22		
Informed Consent d	X																
Demographics	X																
Medical History e	X																
Eligibility Eval.	X	X															
Performance Status	X		X					X								X	
Physical Exam	X		X					X								X	
Height, Weight & Vital Signs f	X		X					X								X	
Clinical Chemistry	X		X g			X		X	X g			X		X		X	
Hematology	X		X h		X	X	X	X	X h		X	X	X	X	X	X	X
Urinalysis	X		X g						X g							X	
ECG	X		X i		X j											X	
Pregnancy test k	X		X					X									
Randomization l		X															
Tumor Assessment m	X m2												X		X m1,m2	X m1	
Tumor Testing n		X															
PK o			X		X												
G1T28 or Placebo p			X	X	X				X	X	X						
Carboplatin			X						X								
Etoposide			X	X	X				X	X	X						
FACT-L and FACT-An q			X				X		X				X		X		
Immunologic Marker r			X												X	X	
AEs s	X									X							
Con. Medications	X									X							
Survival Follow-up c																	X

AE = adverse event; ECG = electrocardiogram; FACT-AN = Functional Assessment of Cancer Therapy – Anemia quality of life instrument; FACT-L = Functional Assessment of Cancer Therapy – Lung quality of life instrument; PRO = patient reported outcome; Eval. = evaluation; PK = pharmacokinetics

- a G1T28 or placebo + E/P therapy will continue until disease progression, unacceptable toxicity, or discontinuation by the patient or investigator (eg, after completing 6 cycles). The tumor should be assessed after every even cycle. Assessments should be performed within 7 days of starting the subsequent cycle.
- b Patients will return to the study center for a Post-Treatment Visit at 30 days (+ 3 days) after the last dose of study drug.

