#### **10.6. Post-Treatment Visit**

Patients will return to the study center for a Post-Treatment Visit within 30 days from the last dose (+ 3 days). The following procedures will be performed at this visit:

- ECOG performance status evaluation
- Physical examination
- Weight and vital signs measurements
- Clinical chemistry, hematology, and urinalysis tests
- Electrocardiogram
- Tumor assessment (obtain tumor assessment by CT scan or MRI for patients who have not progressed at the time of study drug discontinuation [may be performed within 4 weeks]); see details in [Section 11.5.1](#))
- Brain scan with contrast (obtain brain scans by MRI or CT for patients who have not progressed at the time of study drug discontinuation [may be performed within 4 weeks])
- FACT-L and FACT-An Questionnaires
- Immunologic markers blood sample collection (**Part 2 only**)

For patients who have a confirmed CR, it is strongly recommended that they receive PCI after completion of chemotherapy. Patients with a confirmed partial response should also consider PCI after completion of chemotherapy based on the investigator's judgment.

After completing the Post-Treatment Visit, patients will enter the long-term Survival Follow-up Phase.

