### **13.4. Efficacy Analysis**

#### **13.4.1. Efficacy Endpoints**

Unless otherwise stated, the terminology ‘hematologic parameters’ refers to ANC, lymphocyte, hemoglobin, and platelet counts; the terminology ‘hematologic toxicities’ refers to neutropenia, lymphopenia, anemia, and thrombocytopenia. Each parameter and toxicity will be evaluated individually, but are described as such to avoid repetition. Hematologic toxicities are assigned based on CTCAE, Version 4.03.

- Hematologic kinetic endpoints:
  - Change and percent change in hematologic parameter values from baseline to the Post-Treatment Visit
  - Change and percent change in hematologic parameter values from predose for a particular cycle to the end of that cycle
  - Change and percent change in hematologic parameter values from predose for a particular cycle to nadir for that cycle
  - Rate of change in hematologic parameter values from predose for a particular cycle to nadir for that cycle
  - Change and percent change in hematologic parameter values from nadir for a particular cycle to the end of that cycle
  - Rate of change in hematologic parameter values from nadir for a particular cycle to the end of that cycle
  - Area under the curve in hematologic parameter values from predose for a particular cycle to the end of that cycle
  - Area under the curve in hematologic parameters from predose for a particular cycle to nadir for that cycle
  - Area under the curve in hematologic parameter values from nadir for a particular cycle to the end of that cycle
  - By cycle and overall study hematologic parameter nadir values
  - Time to hematologic parameter value nadir by cycle
  - Time to return to predose hematologic parameter values by cycle
  - Proportion of patients with a return to predose hematologic parameter values by cycle
- Hematologic toxicity endpoints:
  - Incidence of Grade 3 and 4 hematologic toxicities
  - Total number of Grade 3 and 4 hematologic toxicities
  - Proportion of patients with a hematologic toxicity recovery by cycle
  - Time to hematologic toxicity recovery by cycle

- Chemotherapy exposure and compliance endpoints:
  - Duration on treatment
  - Number of cycles received
  - Dose intensity and cumulative dose
  - Incidence of dose interruptions, delays, and reductions
  - Incidence of dose delays due to hematologic toxicity
  - Incidence of study treatment termination due to hematologic toxicity
  
- Other efficacy endpoints:

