2.2. Study Design

[figure not shown]
This is a randomized, double-blind, placebo-controlled, multicenter, Phase 1b/2a study of the safety and PK of G1T28 in combination with E/P therapy for patients with newly diagnosed extensive-stage SCLC. The study consists of 2 parts: Part 1 will be a limited Phase 1b, open-label, dose-finding portion followed by a Phase 2a, open-label, expansion portion in up to 18 patients at the selected dose to be used in Part 2. Prior to initiating Part 2, up to a total of 24 patients will be enrolled at the chosen Part 2 dose (6 patients in the dose-finding portion of Part 1 and up to 18 patients in the Phase 2a, open-label, expansion portion of Part 1). Part 2 will consist

of a randomized, double-blind cohort (70 patients will be randomly assigned to G1T28 administered IV with E/P therapy or placebo administered IV with E/P therapy). All parts of the study include 3 study phases: Screening Phase, Treatment Phase, and Survival Follow-up Phase. The Treatment Phase begins on the day of first dose with study treatment and completes at the Post-Treatment Visit.

Part 1

Part 1 starts with a dose finding portion which will be followed by an expansion portion. The goal of the Phase 1b dose-finding portion of Part 1 is to assess the safety, including dose-limiting toxicities (DLTs) and PK of G1T28 administered at a starting dose of 200 mg/m² once daily on Days 1 to 3 of E/P therapy. DLTs are defined in Protocol section 6.1.1.1. The schema of Part 1 is shown in Figure 1.

Figure 1 Study Schema: Part 1

[figure not shown]
E/P = etoposide + carboplatin

- Safety and PK data from Cycle 1 will be considered in making dose escalation/de-escalation decisions (if required) and enrolling additional cohorts
- G1T28 + E/P will continue until disease progression, unacceptable toxicity, or discontinuation by the patient or investigator (eg, after completing 6 cycles). The tumor should be assessed after every even cycle using Response Evaluation Criteria in Solid Tumors (RECIST), Version 1.1. Assessments should be performed within 7 days of starting the subsequent cycle.
- G1T28 will be administered prior to the administration of etoposide and carboplatin on Day 1 and administration of etoposide on Days 2 and 3 of 21-day cycles
- Patients will return to the study center for a Post-Treatment Visit at 30 ± 3 days after the last dose of study drug.

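### SAP Table 20 opens the Post-Treatment window on Day 37, but an on-time Post-Treatment Visit falls on Day 31 to 36 of the last cycle

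*SAP*

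**What the plan says.** Protocol Table 9-1 (footnote b), repeated in SAP Table 2, schedules the visit: "Patients will return to the study center for a Post-Treatment Visit at 30 days (+ 3 days) after the last dose of study drug". Protocol 10.6 instead places it within 30 days of the last dose, with the same 3-day allowance. The note to SAP Figure 1 reads: "Patients will return to the study center for a Post-Treatment Visit at 30 ± 3 days after the last dose of study drug". Protocol 10.6 adds: "After completing the Post-Treatment Visit, patients will enter the long-term Survival Follow-up Phase".

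SAP 6.1.3 bases visit-based summaries on windowed visits, counted from Day 1 of each cycle. The Post-Treatment window is "the first dose date of the last cycle + 36 to last assessment date prior to the start of survival follow-up". The last cycle ends on Day 36, and the note to Table 20 says of hematology: "Hence, for the last cycle, the window for EOC is 19-36". Where several visits share a window during treatment, "the visit closest to the scheduled day will be assigned to the windowed visit".

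Only vital signs (SAP 5.2.2) and ECG (SAP 5.2.4) are summarized by visit as collected. Protocol 13.4.1 lists as a hematologic kinetic endpoint: "Change and percent change in hematologic parameter values from baseline to the Post-Treatment Visit". Protocol 13.4.2.1 also asks for by-visit tabulations that run through this visit. SAP Section 7 does not list either among the removed analyses.

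**The concern.** The last-cycle windows run to the last day on which the Post-Treatment Visit can be on time, and the Post-Treatment window opens only after that. A patient who follows the schedule exactly is therefore left out of the Post-Treatment summary, while a patient who comes late is included.

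The outputs at stake are the baseline-to-Post-Treatment change in blood counts and the Post-Treatment FACT, chemistry and ECOG summaries. Followed literally, Table 20 gives these a nearly empty column made up of late attenders. It can also place Day 31 to 36 values under end-of-cycle, Day 15 or Day 10 labels. Such relabelling is foreseeable, because after study drug stops the remaining in-cycle assessments, including the Day 22 blood count, are only encouraged (Protocol 6.1.3 and 10.8).

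**Working it through.** **Inputs**
- Day 1 is the first study drug day of the cycle (SAP Section 5 definitions; SAP 6.1.3). A date k days after the first dose date is therefore Day k + 1.
- The last dose is on Day d = 1, 2 or 3 (dosing on Days 1 to 3, Protocol 8.1).
- The visit is k = 30, 31, 32 or 33 days after the last dose (Protocol Table 9-1).

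**The plan's own figure.** Day 36 as the end of the last cycle is reproduced by d + k = 3 + 33 = 36. It is the latest compliant visit day, so the cycle-end rule takes in the whole on-time range.

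**On-time visit days, d + k**

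| Last dose | On-time visit | Days at or after Day 37 |
|---|---|---|
| Day 1 | Day 31 to 34 | 0 of 4 |
| Day 2 | Day 32 to 35 | 0 of 4 |
| Day 3 | Day 33 to 36 | 0 of 4 |

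**Window opening.** First dose date + 36 is Day 36 + 1 = Day 37. Overlap with on-time visits: 0 of 12 combinations. The 12 are an unweighted grid, not an expected share of patients.

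**Window closing.** The window ends at the last assessment before survival follow-up. Under Protocol 10.6 that phase follows completion of the Post-Treatment Visit, so for an on-time patient the last assessment is the visit itself, on Day 31 to 36. The window closes before it opens.

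**Sensitivity to wording**
- Within 30 (+3) days: latest day 3 + 33 = 36, so none reaches Day 37.
- 30 ± 3 days: from 1 + 27 = 28 to 3 + 33 = 36, so none reaches Day 37.
- "+36" read as Day 36: only d = 3 with k = 33 qualifies, 1 of 12, and that day also lies in the 19 to 36 end-of-cycle window.

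**Where on-time values go under 30 (+3)**

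| Data | Window that captures Day 31 to 36 | Scheduled day | Distance in days |
|---|---|---|---|
| Hematology | End of cycle, 19 to 36 | 22 | 31 − 22 = 9 to 36 − 22 = 14 |
| Chemistry | Day 15, 12 to end of cycle | 15 | 31 − 15 = 16 to 36 − 15 = 21 |
| FACT | Day 10, 1 to end of cycle | 10 | 31 − 10 = 21 to 36 − 10 = 26 |
| ECOG | None (Day 1 windows only) | – | – |

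A value taken on the scheduled day always displaces the on-time Post-Treatment value. If there is no nearer value, the Post-Treatment value takes that window's label.

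**The case against.** The day count is not in dispute; the counter-case concerns reach and consequence.

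- **Other summaries pick the values up.** SAP 6.2.8 also summarizes continuous safety variables at end of treatment and end of study, using the last non-missing value. An on-time hematology, chemistry or ECOG value would often be that value. This stands as a limit on the harm. It does not restore the Post-Treatment column, does not cover FACT, and does not cover efficacy hematology, which SAP 5.1.1.10 takes from windowed visits.
- **Safety laboratory tables may not need the column.** SAP 6.2.8.2 asks for visits during the treatment period, which ends on Day 36. That is correct, so for hematology the need rests mainly on Protocol 13.4.1 and 13.4.2.1, which SAP Section 7 leaves in place.
- **A last dose after Day 3.** Protocol 13.2.3 foresees within-cycle delays. A last dose on Day 4 gives Day 34 to 37, so one of four compliant days would qualify. But Protocol 8.1 limits the gap between successive doses to 28 hours. Two gaps give at most 56 hours, and 72 − 56 = 16, so the third dose reaches Day 4 only if the first is given at 16:00 or later and the gaps are at or near the limit. This is exceptional.
- **Table layout.** In the text available, the Post-Treatment entry of Table 20 sits on the chemistry row, so its span over other rows is inferred. The sentence in SAP 6.1.3 gives the same window without restricting it to a parameter.
- **The ± sign.** It appears in one SAP figure note only and may be a reading error. Nothing here depends on it.
- **Premature discontinuation.** SAP 6.1.3 says such a visit will be slotted accordingly, but gives no rule that returns it to the Post-Treatment column.

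**Conclusion.** The concern holds. When the last dose is on Day 1 to 3, as the dosing schedule provides, no on-time Post-Treatment Visit enters the Post-Treatment window: 0 of 12 combinations, or 1 of 12 on the most lenient reading. The result is the same under all three wordings of the visit timing. It assumes that Day 1 is the first dose date and that the window in SAP 6.1.3 applies to every windowed parameter.

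The damage is confined to windowed by-visit summaries of hematology, chemistry, FACT and ECOG at Post-Treatment, and to possible mislabelling in the last cycle. Vital signs and ECG are not windowed. Urinalysis is listed only, and all data remain in the listings. Event-based, worst-grade, tumor response, PFS and OS analyses are unaffected. The affected summaries are descriptive, so the result would be a wrong or near-empty column rather than a wrong comparison between arms. It should be corrected, because the rule fails when followed exactly and the repair is simple.

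**What to change.** In SAP 6.1.3 and Table 20:
1. Assign Post-Treatment assessments by the Post-Treatment Visit label in the eCRF, whatever the study day. The documents do not describe that label, but the by-visit, as-collected summaries of vital signs and ECG presuppose one.
2. Exclude those assessments from the last-cycle end-of-cycle, Day 15 and Day 10 windows. State whether the last-non-missing end-of-cycle value in SAP 6.2.8 also excludes them, so that the last cycle does not carry two different end-of-cycle values.
3. Keep Day 36 as the end of the last cycle for counting events and for unlabelled or unscheduled in-cycle assessments.
4. State that the survival follow-up window, which is counted from the post-treatment date, starts from the actual visit date.
5. Reconcile the wordings of the visit timing in Protocol Table 9-1, Protocol 10.6 and the SAP Figure 1 note.

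The cost is an edit to the text, the table and its note, and the windowing program, preferably before unblinding. No new data are needed.
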